5.2 Demographic and Baseline-related Definitions

Age

Age at baseline is the subject's baseline age at the parent study. Age at enrollment is the subject's age in years as recorded on Demographics eCRF of the parent study.

Baseline Lipid and Lipid-related Parameters

Baseline values for lipids (total cholesterol, HDL-C, non-HDL-C, LDL-C, VLDL-C, and triglycerides), ApoA1, ApoB, hsCRP, Lp(a) and their derived parameters (eg, ratio between them) are defined as the two most recent non-missing concentrations measured through central lab prior to or on the **parent** study randomization date. If for only reason only 1 value is available, then that value will be used as baseline.

Change (absolute change) From Baseline

The arithmetic difference from baseline at a given time point:

Change from baseline = (value at given time point – baseline value)

Percent Change From Baseline

The percent change from baseline for a given variable at a given time point is defined as: $100 \times (\text{change from baseline} / \text{baseline value})$

Baseline Metabolic Syndrome

Baseline metabolic syndrome is defined as the eCRF data of history history of metabolic syndrome at **parent** study baseline.

Baseline Major Risk Factors

Baseline major risk factors are defined at FOURIER study baseline:

- Diabetes (type 1 or type 2)
- Age ≥ 65 years at randomization in parent study (and ≤ 85 years at time of informed consent in parent study)
- MI or non-hemorrhagic stroke within 6 months of screening in parent study
- Additional diagnosis of myocardial infarction or non-hemorrhagic stroke excluding qualifying MI or non-hemorrhagic stroke
- Current daily cigarette smoking

- History of symptomatic PAD (intermittent claudication with ABI < 0.85, or peripheral arterial revascularization procedure, or amputation due to atherosclerotic disease) if eligible by MI or stroke history

Baseline Minor Risk Factors

Baseline minor risk factors are defined at **parent** study baseline:

- History of non-MI related coronary revascularization
- Residual coronary artery disease with \geq 40% stenosis in \geq 2 large vessels
- Most recent HDL-C < 40 mg/dL (1.0 mmol/L) for men and < 50 mg/dL (1.3 mmol/L) for women by central laboratory before randomization
- Most recent hsCRP > 2.0 mg/L by central laboratory before randomization
- Most recent LDL-C \geq 130 mg/dL (3.4 mmol/L) or non-HDL-C \geq 160 mg/dL (4.1 mmol/L) by central laboratory before randomization
- Metabolic syndrome

Other Baseline Values

Other baseline values are defined at FOURIER study baseline.

For targeted concomitant medications data, the medication taken at baseline is defined as the medication collected at day 1 visit (ie, currently medications taken at time of day 1 visit) in **parent** study.

For all other variables, the baseline value is defined as the last non-missing value collected prior to or on randomization date in **parent** study.

5.3 Other Study Related Definitions

Treatment-emergent adverse event

Events are categorized as Adverse Events (AEs) or **Disease-related Events (DREs)** starting on or after first dose of investigational product as determined by the flag indicating if the event started prior to the first dose on the Events eCRF and up to the EOS/Safety Follow-up visit or 30 days after the last administration of evolocumab, whichever is earlier.

Treatment-Emergent Disease-Related Events

Events categorized as Disease-related Events (DREs) defined in Protocol Section 9.1.1 starting on or after first dose of investigational product as determined by the flag indicating if the disease-related event started prior to the first dose on the Events eCRF and up to the EOS/Safety Follow-up visit or 30 days after the last administration of evolocumab, whichever is earlier.

Analytical Study Week Assignments

Analytical windows will be used to assign parameters to study weeks. The algorithm is provided in [Appendix A](#).

Investigational Product (IP)

Investigational product includes evolocumab 140 mg every two weeks (Q2W) and 420 mg monthly (QM).

IP Exposure Period in Months (Parent study)

For subjects whose last IP dose is Q2W:

IP exposure period = [min(last IP dose date in parent study + 14 days, EOS date) – first IP dose date in parent study + 1] / 365.25 x 12

For subjects whose last IP dose is QM:

IP exposure period = [min(last IP dose date in parent study + 28 days, EOS date) – first IP dose date in parent study + 1] / 365.25 x 12

IP Exposure Period in Months (For OLE period)

For subjects whose last IP dose is Q2W:

IP exposure period in OLE period = [min(last IP dose date in OLE period + 14 days, EOS date) – first IP dose date in OLE period + 1] / 365.25 x 12

For subjects whose last IP dose is QM:

IP exposure period in OLE period = [min(last IP dose date in OLE period + 28 days, EOS date) – first IP dose date in OLE period + 1] / 365.25 x 12

IP Exposure Period in Months (For the combined parent and OLE periods)

For each subject, IP exposure in combined periods is the sum of the IP exposure in the parent study (defined above) plus the IP exposure in the OLE period (defined above).

Study Exposure Period in Months (Parent study)

For each randomized subject, study exposure period = [(EOS date in parent study – Randomization date) + 1] / 365.25 x 12

Study Exposure Period in Months (For OLE period)

For each subject, study exposure period in OLE period = [(EOS date – enrollment date) + 1] / 365.25 x 12

Study Exposure Period in Months (For the combined parent and OLE periods)

For each subject, study exposure in combined periods is the sum of the study exposure in the parent study (defined above) plus the study exposure in the OLE period (defined above).

Reflexive Approach for LDL-C and VLDL-C

For all analyses related to LDL-C and VLDL-C, unless specified otherwise, an LDL-C reflexive approach will be used. When calculated LDL-C is less than 40 mg/dL or triglycerides are > 400 mg/dL, the ultracentrifugation (UC) LDL-C value and UC VLDL-C value from the same blood sample will be used instead, if available.

Two Consecutive LDL-C Values < cutoff (25 mg/dL and 40 mg/dL) The algorithm for defining the 2 consecutive LDL-C values < 25 mg/dL / 40 mg/dL separated by at least 21 days within OLE study period is summarized below:

- 1) For each blood sample draw date that has at least one LDL-C value within OLE study period, identify the lowest LDL-C value
 - a. If UC values exist regardless of the presence of calculated LDL-C values, the lowest UC LDL-C value will be used
 - b. If only calculated LDL-C values exist, the lowest calculated LDL-C value will be used
- 2) If a subject has 2 consecutive (separated by at least 21 days) LDL-C values that are < 25 mg/dL / 40 mg/dL within OLE study period, then the subject will be considered as a subject with two consecutive LDL-C values < 25 mg/dL / 40 mg/dL within OLE study period.

Two consecutive LDL-C in the parent study has been defined and derived in the same way as above.

6. Analysis Sets

6.1 OLE Safety Analysis Set

The OLE safety analysis set includes all subjects who received at least 1 dose of open-label evolocumab in the OLE study.

7. Planned Analyses

7.1 Interim Analysis and Early Stopping Guidelines

Interim analysis will be performed to support safety data reporting and assessments of other listed endpoints.

7.2 Primary Analysis

Primary analysis activities are commenced based on achieving the EOS milestone described in Protocol Section 3.5.2.

8. Data Screening and Acceptance

8.1 General Principles

The objective of the data screening is to assess the quantity, quality, and statistical characteristics of the data relative to the requirements of the planned analyses.

8.2 Data Handling and Electronic Transfer of Data

The Amgen Global Study Operations-Data Management (GSO-DM) department will provide all data to be used in the planned analyses. This study will use the RAVE database.

All data collected in the eCRF will be extracted from RAVE. Protocol deviations will be transferred from eClinical. Details on data transfer will be provided in the Data Transfer Plan.

8.3 Handling of Missing and Incomplete Data

8.3.1 Patterns of Missing Data

Subjects may be missing specific data points for various reasons. In general, data may be missing due to a subject's early withdrawal from study, a missed visit, or non-evaluability of a data point or an endpoint at a particular point in time. All attempts will be made to capture missing or partial data for this trial prior to the data cutoff date.

The frequency and pattern of missing data for selected endpoints will be assessed through descriptive summaries of the measurements over time.

There will be no imputation for missing data other than date imputation described in the next section.

8.3.2 Handling of Missing Data

Missing and partially missing dates will be queried. Partial/missing EOS dates will be imputed as the maximum of (last dose date of IP, vital signs assessments, lab assessments, AE start dates, concomitant medication start dates and imputed EOS date if partially missing). Partial/missing onset dates (reviewed by CEC) of

time-to- first-event endpoints will be imputed using the following algorithm, with the reference date being the enrollment date.

- Impute the missing year as the year of the reference date
- Impute the missing month as January
- Impute the missing day as 1st

Partial/missing start dates of adverse events and disease-related adverse events will be imputed using the following algorithm, with the reference date being the first dose date.

- Impute the missing year as the year of the reference date
- Impute the missing month as January
- Impute the missing day as 1st

If any of the resulting dates are prior to the reference date, the imputed date will be reset to the reference date. Please note for completely missing start dates of adverse-events and disease-related adverse where 'Did event start before first dose of investigational product?' on eCRF is recorded as 'Yes' will not be imputed. In addition, any imputed death dates will be the maximum of (the all adverse event start dates [use imputed event dates if missing], subject EOS dates [use imputed EOS dates if missing], and subject last confirmed survival status date recorded on the survival status eCRF page). For CEC death events and AE death event start dates, missing or partial missing dates will use the imputed death dates.

Adverse events with a valid answer to the question 'Did event start before first dose of investigational product?' on eCRF can be well defined based on the answer regardless of dates being completely or partially missing. Adverse events that cannot be determined as prior to IP or not either by the question above or by the onset date will be counted as treatment-emergent adverse events.

Concomitant medication with completely or partially missing start dates will be queried. After the query is resolved and the date is still incomplete with year only or year and month only, the start date will be imputed as described in [Table 8-1](#) below.

Table 8-1. Imputation Rules for Incomplete Dates

	Missing	Imputation	Exception
--	---------	------------	-----------

Start date	Day	1	Default to Study Day 1 if an event starts the same year and month as Study Day 1
	Day-Month	1-Jan	Default to Study Day 1 if an event started the same year as Day 1

There are two cases for start date is missing:

- **End date is after first dose date or missing (i.e. medication is ongoing), the medication will be considered as being taken at OLE study baseline and post baseline.**
- **End date is prior to first dose date, the medication will not be considered as being taken at OLE study baseline or post baseline.**

Partial/missing start dates of cardiovascular medical history events which occurred during the gap between subjects' EOS date in the parent study and OLE study enrolment date will be imputed as follows for the sensitivity analysis:

- **If day is missing, impute to 1st of the month. If the partial start date is the same month as EOS date in parent study, impute to EOS date in parent study +1**
- **If day and month are missing, impute to 1st Jan of that year. If the partial start date is the same year as parent study EOS date, impute to EOS date in parent study +1**
- **If start date is completely unknown, no imputation and event will not be considered in the gap**

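### The SAP's onset-date rule for fatal adverse events can move an on-treatment event past the end of the treatment-emergent window and out of the primary fatal and serious summaries

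*SAP*

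**What the plan says.** SAP 8.3.2 contains two rules for incomplete adverse event start dates.

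- **General rule.** "Partial/missing start dates of adverse events and disease-related adverse events will be imputed using the following algorithm". It is anchored at first dose. A missing day becomes the 1st, a missing month January and a missing year the year of first dose. A result before first dose is reset to first dose.
- **Rule for deaths.** "For CEC death events and AE death event start dates, missing or partial missing dates will use the imputed death dates". The death date itself is defined by "any imputed death dates will be the maximum of (the all adverse event start dates [use imputed event dates if missing], subject EOS dates", with "subject last confirmed survival status date recorded on the survival status eCRF page" as the third term of the maximum.

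SAP 5.3 defines a treatment-emergent event as one that starts on or after first dose and "up to the EOS/Safety Follow-up visit or 30 days after the last administration of evolocumab, whichever is earlier". SAP 9.5.1 and Table 9-1 restrict the primary summaries to treatment-emergent events, with fatal and serious adverse events as named rows. Protocol 9.1.3 lists a fatal outcome as a seriousness criterion.

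**The concern.** The start date of a fatal adverse event is the onset of the illness that led to death, not the date of death. The two can be months apart, and subjects who stop evolocumab stay in the study to its end (Protocol 3.1, SAP 3.1), so EOS can fall long after the last dose. If the death date stands in for a partial onset date, an illness recorded as starting in a month on treatment can be dated after the window has closed.

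The error runs in one direction. The general rule moves an uncertain onset earlier and tends to keep the event. The fatal rule moves it later and can only push the event out. The less conservative treatment therefore falls on the gravest category of the primary endpoint.

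**Working it through.** The plan states no figure to reproduce here, so the check is of the date logic.

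**Inputs.** Imputed fatal onset = max(adverse event start dates, EOS, last survival status date), from SAP 8.3.2. Window end = min(EOS, last dose + 30), from SAP 5.3. General-rule onset = first day of the recorded month, not before first dose, from SAP 8.3.2.

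**Inequality.** Imputed onset ≥ EOS ≥ window end. The event stays in only if the imputed onset equals EOS and EOS ≤ last dose + 30. It leaves if EOS is later than last dose + 30, or if the survival status date or another adverse event start date is later than EOS.

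**Examples.** These are in study days, with dates assumed for illustration. The month of onset is taken as known and the day as missing.

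| Case | True onset | Last dose | EOS | Survival date | Latest other AE start | Window end | Fatal-rule onset | General-rule onset |
|---|---|---|---|---|---|---|---|---|
| A | 490 | 480 | 500 | 500 | 470 | min(500, 510) = 500 | 500, in | 481, in |
| B | 490 | 500 | 620 | 620 | 470 | min(620, 530) = 530 | 620, out | 481, in |
| C | 490 | 480 | 500 | 505 | 470 | min(500, 510) = 500 | 505, out | 481, in |
| D | 1815 | 1810 | 1843 | 1843 | 1700 | min(1843, 1840) = 1840 | 1843, out | 1800, in |
| E | 1815 | 1810 | 1840 | 1840 | 1700 | min(1840, 1840) = 1840 | 1840, in | 1800, in |
| F | 1400 | 365 | 1430 | 1430 | 900 | min(1430, 395) = 395 | 1430, out | 1372, out |

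In cases A to E the true onset lies inside the window. The general rule keeps all five and the fatal rule loses three (B, C, D). Case F began after the window and is rightly excluded under either rule. In case B the recorded month starts on day 481 and is over before day 530, so any day in that month is inside the window. Case D has EOS 33 days after the last dose, within the 30 to 33 days that Protocol Table 3 gives for the follow-up call.

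**If the event stays in.** For a subject's first event in a category, SAP 5.1 counts person-time from first dose to onset. In case A that is 500 days rather than 490. In case E onset moves from day 1815 to day 1840. With years of 365.25 days (an assumption), year 5 ends at 5 × 365.25 = 1826.25, so the event moves from the fifth yearly interval to the sixth. If the event drops out and the subject has no other in that category, the subject counts as event-free with person-time to the window end.

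**Scale.** The documents give neither the number of fatal events nor the share with partial onset. Suppose 1% to 5% of 1600 subjects have a fatal treatment-emergent event: 0.01 × 1600 = 16 and 0.05 × 1600 = 80. Suppose also that 2% to 5% of these have a partial onset: 16 × 0.02 = 0.3 and 80 × 0.05 = 4. On those assumptions 0.3 to 4 events are exposed to the rule. This is an upper bound, because one of the timing conditions must also hold. Losing one event would lower the fatal count by 1/16 = 6.25% to 1/80 = 1.25%.

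**The case against.** **Known death date.** The SAP may create an imputed death date only when the date of death is itself incomplete, and Protocol 7.2.2 asks sites to obtain and report that date. With a known death date and a partial onset, the general rule might govern. The SAP does not settle this. A reader might infer that every fatal event with a partial onset and EOS more than 30 days after the last dose is wrongly lost. The text does not support that, both for this reason and because some onsets truly fall after the window. Using the actual death date as onset would not cure the problem, however: if the death in case B were on day 620, it would still be out.

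**Meaning of the phrase.** The start date of an adverse event death could mean the date of a death entered as an event. Against that, the form in Protocol Appendix B asks for the cause of death and does not accept death as a term, so the recorded start is the onset of the cause.

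**First-dose flag.** SAP 8.3.2 says events with a valid answer "can be well defined based on the answer regardless of dates being completely or partially missing". The question asks only whether the event began before first dose. The default to treatment-emergent in the same section likewise covers only uncertainty about that point. Neither addresses the end of the window, though an analyst could read the flag more broadly.

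**Few events, and deaths still reported.** This largely stands. Dates are queried before imputation, serious adverse events are reported within 24 hours (Protocol 9.2.2.2), and all deaths go to the CEC. A reader might infer that deaths vanish from the report. They do not: SAP 9.5.3 summarises positively reviewed deaths by cause, and SAP 5.1 counts mortality events to the later of EOS and last known survival status. A subject with another treatment-emergent serious event also stays in the overall serious row.

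**Consistency with the parent study.** The SAP's summary of changes gives this as the reason for adding imputation of CEC and death dates. It supports the rule for dates of death and mortality endpoints. It is a weaker reason for moving adverse event onset in the OLE-only primary analysis.

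**Conclusion.** The point holds as a conditional defect in the wording. As written, SAP 8.3.2 allows a fatal adverse event with a partial onset date to be placed after the treatment-emergent window, even when the recorded month shows onset on treatment. It then drops out of the primary fatal and serious summaries. An event that stays in can still be dated late, which affects person-time and the yearly intervals. This rests on reading the sentence as governing the onset of fatal adverse events. The SAP is unclear when the death date is complete.

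The number of events is unknown and probably small, and the counts under Scale are illustrations. The matter is minor in size, but it is one-directional, concerns the most serious row of the primary endpoint and is cheap to correct.

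**What to change.** Amend SAP 8.3.2 as follows.

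- Limit the imputed death date to dates of death and CEC mortality endpoints.
- Impute a partial onset of a fatal adverse event by the general rule: the earliest date consistent with the recorded month and year, not before first dose and not after death.
- If the onset date is completely missing, count the event as treatment-emergent unless the first-dose flag is Yes, so that status is never lost through an imputed date. State which date then enters person-time, because the general rule would place such an event at first dose.

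The cost is a few sentences in the SAP and no new data. It departs slightly from the parent-study date rule, which a footnote to the combined analyses can record. The fatal count may rise slightly, and some events with only a year or no date at all may be counted although they began after the window. For a safety endpoint that is the more acceptable direction of error.

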8.4 Detection of Bias

Important protocol deviations likely to impact the analysis and interpretation of the endpoints will be tabulated in the Clinical Study Report (CSR).

If any sensitivity analyses are required to evaluate potential biases in the study's conclusions, the sources of the potential biases and results of the sensitivity analyses will be documented in the CSR.

8.5 Outliers

Various methods, including univariate summaries, histograms, scatter plots, box plots, and line graphs, will be used to identify outliers in key variables. Extreme data points will

be identified during the review of the data prior to database snapshot. Such data points will be reviewed with clinical data management to ensure accuracy. Unless specified otherwise, all analyses will include outliers in the data. Sensitivity analyses may be undertaken if extreme outliers for a variable are observed.

8.6 Distributional Characteristics

There are no distributional requirements for the planned analyses. Therefore, no assessment will be made.

8.7 Validation of Statistical Analyses

Programs will be developed and maintained, and output will be verified in accordance with current risk-based quality control procedures.

Tables, figures, and listings will be produced with validated standard macro programs where standard macros can produce the specified outputs.

The production environment for statistical analyses consists of Amgen-supported versions of statistical analysis software; for example, the SAS System version 9.4 or later.

9. Statistical Methods of Analysis

9.1 General Considerations

Statistical analyses in this open-label study are descriptive in nature. No formal hypothesis will be tested in this study. No statistical inference is planned.

Subject disposition, demographics, and baseline characteristics and exposure to IP will be summarized.

Summary statistics for continuous variables will include the number of subjects (n), mean, standard deviation (SD) or standard error (SE), median, the first (Q1) and third (Q3) quartiles, minimum, and maximum. For categorical variables, the frequency and percentage will be given. The baseline value is defined as the subject's baseline value from the **parent** study as defined in [Section 5.2](#), unless specified otherwise. All analyses will be performed on the OLE safety analysis set.

Interim and final analyses will be based on data collected from this study combined with the data from the FOURIER study as applicable. For all endpoints, results will be summarized by the randomized treatment group from the parent study and overall, unless specified otherwise.

All deaths and cardiovascular events of interest (MI, stroke, coronary revascularization, hospitalization for unstable angina, hospitalization for heart failure, and TIA) will be reviewed by an independent external CEC, using standardized definitions. The CEC is external to Amgen and primarily comprises both academic clinical physicians (to include cardiologists) and medical reviewers trained on the clinical trial protocol, the CEC charter, and CEC processes. The chairman of the CEC is responsible for overseeing the operations in conformance with the CEC charter and for supervising the flow of data between the sponsor/data management and the CEC. Committee members are qualified in the appropriate subspecialty and free of conflict of interest. The CEC reviews events according to pre-specified criteria defined in the CEC charter. The CEC will be blinded to the original randomized treatment group from the **parent** study.

There will be no imputation for missing data other than date imputation described in [Section 8.3.2](#)

